3.4.1.1 Major Protocol Deviations Assessment

Prior to unblinding, the medical and operational leads will jointly assess protocol deviations and create a consensus final protocol deviations assessment file. Protocol deviations deemed to indicate clear violations of GCP and/or subject consent; or to have a likely effect on the primary immunogenicity outcomes will exclude those subjects from the PP analysis set. In general, the following will be deemed "major:"

- Failure to obtain completely executed and documented informed consent.
- Failure to receive, or document receipt of, the study treatment as randomized.
- For inclusion in the PP Population, failure to provide a sample for serologic analysis on Day 0 and on Day 21.
- Receipt of immunosuppressive medication from Day 0 until the Day 21 visit.
- Other deviations deemed likely by the Sponsor to degrade the immune response to the test article.

4 SUBJECT DISPOSITION

The number of subjects consented, randomized, and vaccinated will be presented by treatment group for all subjects.

The number (percentage) of subjects who have completed the study through Day 21 and through Day 364 will be presented by treatment group for all subjects in the Safety Population. The number of subjects who discontinue the study prior to Day 364 and the reason for discontinuation (eg, withdrawal of consent, lost to follow-up, death, etc.) will be presented. Study completion status through Day 21 will be determined based on completion of the Day 21 visit, and study completion status through Day 364 will be determined based on the End of Study (EOS) electronic case report form (eCRF).

A listing of all subjects in the Safety Population who are discontinued will be presented by treatment group, reason for discontinuation, and day of last study contact. Day of last study contact will be calculated as follows: date of study discontinuation (as recorded on EOS eCRF) minus date of Day 0 vaccination.

A listing of all subjects in the Safety Population with one or more protocol deviations recorded through Day 21 and through Day 364, will be provided and will include: treatment group, study day associated with the deviation (as provided on the protocol deviation log if available), protocol deviation category (as described below), and a description of the deviation as recorded by the site. All deviations from protocol procedures, evaluations, and visits will be documented throughout the course of the study.

5 DEMOGRAPHICS AND OTHER BASELINE CHARACTERISTICS

Demographic parameters and other baseline characteristics (age at Day 0 vaccination, gender, ethnicity, race, height [cm], weight [kg], as well as history of receipt of 2016 - 17 influenza vaccine will be summarized by each treatment group for all subjects in the Safety Population and ITT Population. Descriptive statistics (number of subjects [N], mean, median, minimum and maximum values) will be presented for weight (kg) and height (cm) measurements recorded at Study Day 0. No statistical testing will be performed on these data.

Age (years) at the Day 0 vaccination will be calculated as the closest lower integer result of (date of Study Day 0 vaccination – date of birth) / 365.25, and will be presented as a continuous variable, using descriptive statistics. Gender will be summarized as a categorical variable (eg, "Male", "Female"). Ethnicity will be summarized as number and percentage of subjects according to predefined categories (ie, Hispanic or Latino, not Hispanic or Latino) listed in the CRF. Race will also be summarized as number and percentage of subjects according to predefined categories (ie, American Indian or Alaska Native, Asian, Black or African American, Native Hawaiian or Other Pacific Islander, and White).

Medical history and physical examination diagnoses/abnormalities will be coded using MedDRA version 20.0. Baseline medical history and physical examination findings recorded on Day 0 (prior to vaccination) will be summarized separately, by MedDRA system organ class (SOC), preferred term (PT), treatment group, and for all subjects in the Safety Population. Within each SOC and PT, the number and percentage of subjects with at least one abnormality in that SOC or PT will be presented, respectively. Multiple abnormalities within a given SOC or PT for a subject will be counted once within that respective SOC or PT.

6 EXTENT OF EXPOSURE

6.1 Study Vaccine

Subject vaccination exposure will be summarized as the number and percentage of subjects who received test article at Day 0. The number of subjects vaccinated at Day 0 will be presented by treatment group and for all subjects. The number of subjects vaccinated by location (right or left deltoid) will be presented in subject data listings.

6.2 Concomitant Medication

The assessment of concomitant medication use by the subject during the study will coincide with the collection period of adverse events; per the protocol, concomitant medication includes prescription and non-prescription drugs or other treatments, and any vaccine other than study vaccines. Concomitant medications recorded on the Concomitant Medications CRF will be summarized by WHO-DRUG Anatomical Therapeutic Chemical (ATC) Term and standardized (generic) medication name version September 2019. The number (percentage) of subjects who record one or more concomitant medications will be presented by treatment group for all subjects in the Safety Population. Multiple occurrences of medication usage for a subject will be counted only once within an ATC term and standardized medication name. The presentation of concomitant medications will include all medications recorded on the Concomitant

Medications CRF, including medications with a missing or partial start date or a start date prior to Study Day 0 vaccination. A separate listing of treatment-emergent new concomitant medications will be presented.

7 ANALYSES ADDRESSING PROTOCOL OBJECTIVES

7.1 Analyses of Primary Objectives of immunogenicity

The analysis of primary immunogenicity endpoints will be conducted by using PP and ITT population, with PP population as the primary analysis. No missing data will be imputed.

Antibody titers specific for the HA receptor binding domains of each of the virus strains included in Tri-NIV, H1N1, H3N2, and Bv, will be analyzed.

- Geometric mean titers (GMT) of Antibody titers specific for the HA receptor binding domains of each of the virus strains and their 95% CIs will be summarized by treatment at baseline (pre-vaccination on Day 0) and post vaccination on Day 21. GMT will be calculated as the antilog of the mean of the log-transformed HAI titers for a given treatment group. Lognormal distribution is assumed for antibody titer to construct confidence interval.
- Between-group geometric mean ratio (GMR_{new/ref}) and its 95% CI for each of the Tri-NIV groups against active comparator group Fluzone HD will be conducted using two-sample t distribution. A sample SAS code is given below:

```
proc ttest data=fludata alpha=0.05;
by Visit;
class grp;
var log(HAI D21);run;
```

• Within-group geometric mean ratio (GMR_{post/pre}) for each arm will be conducted using paired t distribution. A sample SAS code is given below:

```
proc ttest data= fludata_Long alpha=0.05;
by Visit Group;
PAIRED log(HAI D21)*log(HAI D0);run;
```

Seroconversion rate (SCR) is defined as the percentage of subjects with either a baseline HAI titer < 1:10 and a post-vaccination titer ≥ 1:40, or a baseline HAI titer ≥ 1:10 and a 4-fold increase in post-vaccination HAI titer relative to baseline. The 95% confidence interval will be constructed by Clopper-Pearson method with the following sample SAS code:

```
proc freq data=fludata ;
by treatment;
tables seroconvind/ nocum norow binomial;
exact binomial;
run;
```

• Seroconversion rate difference is defined as the difference of seroconversion rates between each of the Tri-NIV vaccine groups and Fluzone HD group. The Chi-Square p-value for testing the equality of SCRs between two groups will be derived with continuity adjustment. The Newcombe method will be used to construct its 95% confidence interval with the following sample SAS code:

```
proc freq data = fludata;
tables trtan*seroconvind / riskdiff (column=2 cl=(newcombe)) chisq;
run ;
```

- Seroprotection rate (SPR) is defined as the percentage of subjects with an HAI titer ≥ 1:40 by treatment group. The 95% confidence interval will be constructed similarly by Clopper-Pearson method.
- Seroprotection rate difference is defined as the difference of SPRs between each of the Tri-NIV groups and Fluzone HD group. The 95% CI will be constructed similarly to that for SCR difference.

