# 3.3 Randomization and Blinding Procedure

Subject randomization will be conducted using an Interactive Web Randomization System (IWRS). Stratification will be by age (60 to < 75 and  $\geq$  75 years), gender, and history of receipt of 2016 - 17 influenza vaccine. Proportions of subjects in the various strata will not be pre-specified; rather, the goal will be to achieve an approximately equal distribution of subjects with these characteristics across the various treatment groups.

Preparation and administration of each test article dose will be performed by unblinded vaccine pharmacists/administrators. These persons, identified prior to trial dosing, will not perform any trial assessments post-dosing.

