1.1 Study Design

This is a Phase 1/2, randomized, observer-blinded, active-controlled trial. Approximately 330 eligible subjects will be enrolled and randomized into 1 of 3 treatment groups as shown in the Trial Design table (Table 1). Each group will consist of approximately 110 subjects total, stratified by age (60 to < 75 and \geq 75 years), gender, and history of receipt of 2016 - 17 influenza vaccine. On Day 0, subjects in Groups A and B will be administered an IM injection of 15 or 60 µg HA per strain of Tri-NIV in a 0.3 or 0.8 mL volume, respectively; subjects in Group C will receive the preconfigured comparator (Fluzone HD) at the manufacturer's recommended dose and volume. On Day 21, all Group A and B subjects will be administered a rescue injection with a licensed seasonal influenza vaccine, while all Group C subjects will be administered an injection Schedule of Events. It is anticipated that a percentage of the randomized trial subjects will not complete the trial. Subjects who withdraw or are discontinued will not be replaced. The maximum duration of the trial will be approximately 1 year for each subject.

Enrollment will be divided into 2 stages. Stage 1 will enroll a group of approximately 60 subjects (approximately 20 subjects per treatment group) and Stage 2 will enroll the remainder of the subjects per treatment group. The only difference in the 2 stages will be a safety review in-clinic visit for Stage 1 subjects on Day 7 (+ 1 day) of the trial, whereat subjects will be asked to present their subject diaries. In Stage 2, a safety review telephone call on Day 7 (± 1 day) of the trial will replace the clinic visit. Progression from Stage 1 to Stage 2 will require favorable review of cumulative Stage 1 safety against vaccination holding rules.

Table 1:Trial Design

		Day 0 Trial ' (non-do	Freatme minant o	nt Injection leltoid)		Day 21 Rescue Injection ^[2] (dominant deltoid)			
Grou p	Vaccine Name	HA Dose per Strain, μg (H1N1/H 3N2/By)	Total HA Dose, ug	Matrix- M1 Adjuvant Dose, µg ^[1]	Injectio n Volume , mL	Vaccine	Stage 1 Subjects [[] 3]	Stage 2 Subjects [[] 3]	Total Subjects per Group
А	Tri-NIV	15 / 15 / 15	45		0.3	Licensed seasonal	20	90	110
В	Tri-NIV	60 / 60 / 60	180	50	0.8	influenza vaccine	20	90	110
С	Fluzone HD	60 / 60 / 60	180	None	0.5	Placebo	20	90	110
				Tota	al Trial Tai	rget Subjects	60	270	330

Note: All subjects will receive 2 vaccinations by IM injection on Day 0 and Day 21.

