1.2 Randomization and Treatment Assignments

After the Subject is deemed by the Principal Investigator (PI) to meet the eligibility criteria and prior to the performance of any study-related assessments, a central randomization system will be used for assigning a subject ID. The subject ID will be used throughout the trial on all related documents such as source documents and electronic case report forms (eCRFs).

At the screening visit, the subject ID will be assigned. At the enrollment visit (Day 0), after the PI has confirmed that the subject meets all of the inclusion criteria and none of the exclusion criteria, subjects will be randomized at a ratio of 1:1:1 into Arms 1 through 3, respectively, using a block randomization design. Randomization will be stratified by age (60 to < 75 and \geq 75 years), gender, and history of receipt of 2016 - 17 influenza vaccine. Stratification for both age, gender and history of 2016 - 17 influenza vaccine group will be controlled by central randomization system.

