7.2 Analyses of Secondary Objectives of Immunogenicity

Antibody titers specific for the HA receptor binding domains of at least 2 historic A virus strains (one H1N1 and one H3N2) as measured by the HAI assay will be summarized as follows using the same statistical approaches as the primary immunogenicity endpoints:

- Geometric mean titer (GMT) defined as the antilog of the mean of the log-transformed HAI titers for a given treatment group.
- Geometric mean ratio (GMR) defined as the ratio of post-vaccination and pre-vaccination HAI GMTs within the same treatment group (designated as GMRPost/Pre).
- Seroconversion rate (SCR) defined as the percentage of subjects with either a baseline HAI titer < 1:10 and a post-vaccination titer \geq 1:40, or a baseline HAI titer \geq 1:10 and a 4-fold increase in post-vaccination HAI titer relative to baseline.
- Seroprotection rate (SPR) defined as the percentage of subjects with an HAI titer \geq 1:40.

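### Randomization is stratified by age, gender and 2016-17 vaccination, but the Tri-NIV versus Fluzone HD comparisons leave the strata out, so their intervals are conservative to the extent that the strata predict response

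*SAP*

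**What the plan says.** SAP 1.2 states that "subjects will be randomized at a ratio of 1:1:1 into Arms 1 through 3, respectively, using a block randomization design", with stratification by age (60 to under 75, 75 and over), "gender, and history of receipt of 2016 - 17 influenza vaccine". That makes 2 x 2 x 2 = 8 strata. Protocol 3.3 leaves the stratum proportions open and gives the purpose: "the goal will be to achieve an approximately equal distribution of subjects with these characteristics across the various treatment groups". On size, SAP 1.1 says "Each group will consist of approximately 110 subjects total".

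The comparisons with Fluzone HD are in SAP 7.1:

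- The between-group GMR and its 95% CI "for each of the Tri-NIV groups against active comparator group Fluzone HD will be conducted using two-sample t distribution". The sample code has no strata terms.
- The SCR difference is coded as "tables trtan*seroconvind / riskdiff (column=2 cl=(newcombe)) chisq", a single 2 x 2 table per comparison with a Newcombe interval and a chi-square.
- For the SPR difference, "The 95% CI will be constructed similarly to that for SCR difference".

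SAP 7.2 analyses the secondary HAI endpoints "using the same statistical approaches as the primary immunogenicity endpoints", and SAP 7.3 does likewise for the exploratory endpoints. Protocol 10.4.1.2 also specifies an unstratified Newcombe interval for the SCR and SPR differences. It gives no method for a between-group GMR, which appears only in the SAP.

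SAP 12.2 rules out adjustment for pre-vaccination titer. It does not mention the stratification factors, and neither document brings them into any analysis or says why they are left out.

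**The concern.** Blocking within strata makes the groups nearly equal in age group, gender and vaccination history. Chance imbalance in those factors then contributes almost nothing to the sampling error of a between-group difference. A plain two-sample t interval and an unstratified Newcombe interval estimate their variance from the total spread within each group, which still includes the spread between strata. If the strata are related to titer or seroconversion, the standard error is overstated.

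Precision is what is at stake. The trial has no formal hypothesis, so the intervals are its comparative result, and SAP 9 says the data are to guide later development and dosing. The point is separate from adjustment for baseline titer: it concerns factors that the design already uses, and it affects the SCR and SPR differences as well as the GMR.

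**Working it through.** **The plan's own figure.** Neither document states a CI width or coverage. The only between-group figure is in SAP 9: non-inferiority power of 46% at a 70% rate and 41% at 50%, with 100 per group and margin -0.10. With an unstratified variance and one-sided 0.05 (z = 1.645):

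- 70%: SE = sqrt(2 x 0.7 x 0.3 / 100) = 0.0648; Phi(0.10/0.0648 - 1.645) = Phi(-0.102) = 45.9%.
- 50%: SE = sqrt(2 x 0.5 x 0.5 / 100) = 0.0707; Phi(1.414 - 1.645) = 40.9%.

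Both reproduce, so this figure takes no account of the strata either.

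**GMR interval.** Inputs from the documents: 1:1:1 blocked allocation within strata (SAP 1.2), n of about 110 per group (SAP 1.1), two-sided 95%. Assumed: R2, the share of log-titer variance explained by the strata.

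- Variance that the two-sample t estimates: 2 x sd^2 / n.
- Actual variance under stratified blocks: (1 - R2) x 2 x sd^2 / n.
- Width ratio = 1/sqrt(1 - R2). Coverage = 2 x Phi(1.96/sqrt(1 - R2)) - 1.

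| R2 (assumed) | Width ratio | Coverage | Simulated coverage, plain t | Simulated coverage, strata in model |
|---|---|---|---|---|
| 0 | 1.000 | 95.0% | 94.6% | 94.6% |
| 0.05 | 1.026 | 95.6% | 95.4% | 94.8% |
| 0.10 | 1.054 | 96.1% | 95.7% | 94.7% |
| 0.20 | 1.118 | 97.2% | 97.2% | 95.3% |

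The simulation used 5,000 trials of 330 subjects, 8 strata, blocks of 6 (block size is not stated) and assumed factor prevalences of 25%, 55% and 65%. Monte Carlo error is about sqrt(0.95 x 0.05 / 5000) = 0.3 points. Simulated width ratios matched the formula to within 0.001. With simple instead of stratified randomization at R2 = 0.20, the plain t interval covered 94.7%. The excess coverage therefore comes from stratifying and then not adjusting.

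**A concrete case.** Assume 70% vaccinated, 25% aged 75 or over, within-stratum log2 SD 1.6, +1.0 log2 if unvaccinated and -0.5 if 75 or over.

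- Between-stratum variance = 1.0^2 x 0.7 x 0.3 + 0.5^2 x 0.25 x 0.75 = 0.257.
- R2 = 0.257 / (0.257 + 1.6^2) = 0.091, and the width ratio = 1/sqrt(0.909) = 1.049. Simulation also gave 4.9%, with coverage of 96.0% against 95.0%.
- Adjusted half-width at 110 per group = 1.97 x 1.6 x sqrt(2/110) = 0.425 log2. At a true ratio of 1 the interval is about 0.74 to 1.34 adjusted and 0.73 to 1.36 unadjusted.
- With weaker strata effects the simulated excess width was 1.2%.

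**SCR and SPR differences.** Assume SCR of 60% in unvaccinated and 30% in vaccinated subjects, 10 points lower at 75 or over.

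- The unstratified Newcombe interval was 3.3% wider than a Mantel-Haenszel interval with the Sato variance, and covered 96.1% against 95.0%. From a half-width of about 12.5 points, that is 12.5 - 12.5/1.033 = 0.4 points.
- A stratified Newcombe interval with Mantel-Haenszel weights recovered nothing: width ratio to the unstratified interval 0.997, coverage about 95.9%.
- With no strata effect, a stratum-weighted interval was about 2% wider than the plain Newcombe interval (ratio of plain to weighted 0.979). At an outcome R2 of 0.046 the two were equal (1.002), and at 0.126 the plain interval was 4.8% wider.

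**The case against.** The strongest reply is that the trial is descriptive. SAP 9 says no hypothesis tests are specified and that the sample size does not support a contrast with Fluzone HD. Simple unadjusted summaries are a legitimate choice in a Phase 1/2 trial, the intervals err on the safe side, and in the concrete case above no reading of the result would change. The facts in this reply are right, and they limit the weight of the point. They do not remove it: with no formal test the intervals carry the comparison, the factors are already available, and no reason is given for leaving them out.

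Three stronger readings are tempting and are not supported.

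- A reader might infer that the 95% intervals are invalid. Coverage is nominal or higher: if the strata predict nothing the intervals are correct, and if they do predict response the intervals are conservative. There is no bias and no type I error inflation. The chi-square that SAP 7.1 plans for SCR would be conservative too; whether it belongs in a plan without hypothesis tests is a separate question.
- A reader might infer that the factors were chosen because they are expected to drive the response. Protocol 3.3 gives balance as the goal and says nothing about prognosis.
- A reader might infer that the benefit of stratifying is thrown away. The point estimates keep the benefit of balance; only the reported standard error fails to reflect it.

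**Conclusion.** The point holds in conditional form. The plan stratifies the allocation, leaves the strata out of every Tri-NIV versus Fluzone HD comparison and gives no reason. For strata R2 between 0 and 0.20, the GMR interval is 0% to 11.8% wider than necessary and covers 95.0% to 97.2%. At R2 of 0.05 to 0.10 the excess is about 3% to 5% of width and roughly one point of coverage or less.

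The SCR and SPR differences are affected in the same direction, by about 3% of width under strong assumed effects and not at all under weak ones.

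Every size here rests on assumed strata effects, prevalences and block size, because the documents give none of them. The direction does not depend on those values, and the consequence is limited to precision. It is a low-cost improvement, not a correction of an invalid analysis.

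**What to change.** In SAP 7.1:

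- Estimate each Day 21 between-group GMR from a linear model on log titer with treatment, age stratum, gender and 2016-17 vaccination.
- Estimate the SCR and SPR differences as Mantel-Haenszel risk differences with the Sato (stratum-based) variance. A stratified Newcombe interval should not be used for this purpose, since it did not recover the precision.
- Prespecify whether the IWRS or the EDC stratum value is used when they differ. SAP 3.4.1 already compares the two to flag randomization errors.
- Prespecify how sparse strata are pooled. Stratum sizes are not fixed in advance, per-protocol exclusions will shrink them, and microneutralization may be run on a subset only.
- Keep the planned t and unstratified Newcombe intervals as sensitivity tables.
- Record the departure from Protocol 10.4.1.2 for the SCR and SPR differences in SAP section 13, which now reads NA.

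The cost is SAP wording, a few lines of code and one more set of tables, with no new data. The downside is a small return: about 1% or less of interval width if the strata effects are weak, and for SCR and SPR an interval up to about 2% wider than the plain Newcombe if there are none.

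### The two sample PROC FREQ blocks for seroconversion in SAP 7.1 target opposite levels of the indicator, so run as written one of them reports the wrong category

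*SAP*

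**What the plan says.** SAP 7.1 defines SCR correctly, as the percentage of subjects who seroconvert, and then turns to code for its interval: "The 95% confidence interval will be constructed by Clopper-Pearson method with the following sample SAS code". The TABLES statement in that block is "tables seroconvind/ nocum norow binomial". It has no LEVEL= option.

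For the between-group comparison, the prose is "Seroconversion rate difference is defined as the difference of seroconversion rates between each of the Tri-NIV vaccine groups and Fluzone HD group", and the sample statement is "tables trtan*seroconvind / riskdiff (column=2 cl=(newcombe)) chisq".

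For the seroprotection rate (SPR), SAP 7.1 gives no code: "The 95% confidence interval will be constructed similarly by Clopper-Pearson method". The SPR difference is handled in the same way. SAP 7.2 and 7.3 carry the primary approaches over to the secondary and exploratory titers.

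For the GMRs, the between-group sample contains "var log(HAI D21);run" and the within-group sample contains "PAIRED log(HAI D21)*log(HAI D0);run". Neither shows a back-transformation. SAP 7.1 mentions the antilog for the GMT only. Protocol 10.4.1.2 exponentiates the GMT and the within-group GMR, but does not mention the between-group GMR. SAP Section 12 says that GMT analyses are on the log10 scale.

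Neither document states how `seroconvind` is coded or how the analysis datasets are laid out.

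**The concern.** Two adjacent blocks analyse the same variable for a primary endpoint and take different levels as the event. The interval block runs without an error message and prints a plausible percentage with a valid exact interval, possibly for the wrong category. Under the other coding, the difference block does the same with the wrong sign.

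Timing adds to this. SAP Section 10 treats the results of the Day 21 unblinded review as final, so the code should be right before that lock. SCR and SPR against the homologous strains are primary immunogenicity endpoints, and the trial is meant to direct later dosing.

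**Working it through.** The plan states no figure for this point, so there is none to reproduce. SAS was not run. The check rests on standard PROC FREQ behaviour: BINOMIAL without LEVEL= describes the first ordered level, and RISKDIFF takes row 1 minus row 2 in the named column.

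**Inputs**
- Event level in the interval block: none named, so level 1 (SAP 7.1).
- Event level in the difference block: column 2 (SAP 7.1).
- Coding of `seroconvind`: not stated; both codings are tried.
- Subjects per arm: about 110 (SAP 1.1).
- Illustrative SCR: 70%, one of the scenarios in SAP Section 9, so 0.70 × 110 = 77 seroconverters.
- Second arm for the difference: 66/110 = 60%, assumed for illustration only.
- Tri-NIV is taken as the first row and Fluzone HD as the second. The SAP does not state this order.

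**Step 1: the two codings side by side** (T = Tri-NIV, F = Fluzone HD)

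| Coding of `seroconvind` | Interval block (level 1) | Difference block (column 2) |
|---|---|---|
| 1st level = no, 2nd = yes | 1 - SCR: wrong category | SCR(T) - SCR(F): right |
| 1st level = yes, 2nd = no | SCR: right | (1 - SCR(T)) - (1 - SCR(F)) = -(SCR(T) - SCR(F)): wrong sign |

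Neither row has both entries right. The first is the coding that column 2 implies.

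**Step 2: size under the first coding.** The Clopper-Pearson limits for x out of n are the 2.5% quantile of Beta(x, n - x + 1) and the 97.5% quantile of Beta(x + 1, n - x).
- Seroconverters, x = 77, n = 110: 70.0%, limits 0.6052 and 0.7837.
- Level 1, x = 110 - 77 = 33: 30.0%, limits 0.2163 and 0.3948.
- Cross-check: 1 - 0.7837 = 0.2163 and 1 - 0.6052 = 0.3948.

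At 90% (99/110), the block gives 10.0% (5.1 to 17.2) instead of 90.0% (82.8 to 94.9). At 50%, both readings give 40.3 to 59.7, so a rate near one half would hide the error.

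**Step 3: size under the reverse coding.** The Newcombe interval for d = p1 - p2 combines the Wilson limits (l, u) of each arm: lower = d - √[(p1 - l1)² + (u2 - p2)²], upper = d + √[(u1 - p1)² + (p2 - l2)²].
- Wilson limits: 77/110 gives 0.609 to 0.778; 66/110 gives 0.507 to 0.687.
- Seroconverter column: d = 0.70 - 0.60 = +10.0 points, interval -2.6 to 22.2.
- Other column (33/110 versus 44/110): d = 0.30 - 0.40 = -10.0 points, interval -22.2 to 2.6.

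**Step 4: the GMR samples.** VAR and PAIRED take variable names, not log() expressions, so these blocks would stop with an error. With log titers computed beforehand, the output is still a log difference. A GMR of 1.5 would appear as ln 1.5 = 0.405, or log10 1.5 = 0.176, until it is back-transformed.

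**The case against.** The strongest reply is that all of this is labelled sample code, beneath prose that gives the right definition and interval method. A programmer who follows the prose gets the right answer. The frequency table prints both percentages, and the correct exact limits are one minus the printed ones. In an arm where every subject seroconverts, the only level is the event and the output is right. The trial is descriptive, and a contradiction between the rate and difference tables would probably be noticed. All of this stands. It limits the point to a code error, but it does not remove the mismatch in code that the SAP itself puts forward for constructing the interval.

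A reader might infer more than the documents support:
- **That the interval block certainly reports non-seroconverters.** This depends on a coding that the SAP never states; it is implied only by column 2.
- **That all SCR and SPR results are affected.** The SPR wording, and the carry-over in SAP 7.2 and 7.3, adopt a method. The error spreads only if the same snippet is reused.
- **That BY Visit separates the Day 0 and Day 21 values that PAIRED needs.** The dataset name suggests one row per visit, but the statement names separate Day 21 and Day 0 variables. The layout is unknown.
- **That the three arms make the comparisons impossible.** Randomization is to three arms ("subjects will be randomized at a ratio of 1:1:1 into Arms 1 through 3, respectively, using a block randomization design") and the samples show no subset, but the prose makes both comparisons pairwise against Fluzone HD.
- **That the GMRs would be silently wrong.** The log() expressions fail visibly. The space in the titer variable names may come from PDF reading, and nothing rests on it.

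**Conclusion.** The point holds as an inconsistency between the two PROC FREQ samples. Run as written, one of them describes the wrong category: either the SCR interval is that of the non-seroconverters (30.0% for 70.0% at 77/110), or the SCR difference is taken on the non-seroconverter column (-10.0 for +10.0 points at 77/110 versus 66/110).

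This rests on the SAS default for BINOMIAL and, for the sign, on Tri-NIV being the first row. With Fluzone HD first and the reverse coding, the two reversals would cancel in the number, although the column would still be the non-seroconverters.

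The estimand, the population and the interval methods are not in question. The GMR samples are a secondary matter. The syntax would fail visibly; the real gap is that neither document states the back-transformation for the between-group GMR.

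**What to change.** In SAP 7.1:
- State the coding of `seroconvind` and of the seroprotection indicator.
- Name the event by value in the interval block, for example `binomial(level='1')` or the formatted 'Yes' level, and confirm that the riskdiff column is the same category. Naming it by position (`level=2`) is fragile, because an arm in which every subject responds has no second level.
- State the row order of treatment, so that the difference reads Tri-NIV minus Fluzone HD.

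As a secondary correction:
- Compute log titers before PROC TTEST.
- Show the subset to each Tri-NIV group versus Fluzone HD, by strain.
- State exponentiation and ratio direction for both the between-group and the within-group GMR. The antilog must match the log base used: SAP Section 12 says log10, whereas log() in SAS is the natural log.

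The cost is a few lines of SAP text and code. No analysis, sample size or data collection changes. The edit should be made before the Day 21 unblinding.
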